6. STUDY DESIGN

6.1. Overview of Study Design

This is a Phase 2, open-label, multiple-dose, dose-escalation study to assess the safety, tolerability, PK, and PD of NBI-74788 in approximately 30 adult female and male subjects (18 to 50 years of age) with a documented medical diagnosis of classic 21-hydroxylase

deficiency CAH. The study will include a sequential-cohort design with 4 NBI-74788 dosing regimens, with each regimen administered for 14 consecutive days:

- Cohort 1: NBI-74788 50 mg once daily with a bottle of vanilla-flavored (~237 mL) at approximately 2200 hours.
- Cohort 2: NBI-74788 100 mg once daily with a bottle of vanilla-flavored (~237 mL) at approximately 2200 hours.
- Cohort 3: NBI-74788 100 mg once daily with the evening meal at approximately 1900 hours.
- Cohort 4: NBI-74788 100 mg twice daily with breakfast at approximately 0700 hours and with the evening meal at approximately 1900 hours.

There will be an approximate 2-week period to evaluate safety and tolerability data before proceeding from Cohort 1 to Cohort 2. Subjects who previously completed the current study in Cohort 1 or Cohort 2 may reenroll to participate in Cohorts 3 or 4 (in addition to new subjects).

Table 1 depicts the cohorts, doses, and number of subjects per cohort.

Cohort	NBI-74788 Dose	Approximate Dosing Time(s)	Number of Subjects
1	50 mg	2200 hours	8-10
2	100 mg	2200 hours	8-10
3	100 mg	1900 hours	8-10
4	100 mg	0700 and 1900 hours	Up to 8

Table 1:Dose Cohorts, Doses, and Number of Subjects

Subjects must provide informed consent prior to any study-related procedures. Subjects will then be screened for eligibility to participate in the study for up to approximately 3 weeks (Days -28 to -8). Subjects who reenroll and have had a stable medication regimen for CAH since their last visit in this study do not have to undergo screening; those who reenroll and have had a change to their medication regimen for CAH must undergo a second screening visit. During screening, subjects will provide a single blood sample in the morning between 0700 and 1000 hours (prior to first morning dose of hydrocortisone) to determine their 17-OHP levels for study entry.

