6.2. Dose Escalation Procedure

Cohort 1 will consist of approximately 8 to 10 subjects who will receive a daily dose of NBI-74788 50 mg at approximately 2200 hours for 14 days (subjects will receive study drug at the site on Days 1, 2, and 14, and self-administer study drug at home on Days 3 to 13). Following the completion of Day 15 assessments for all subjects in Cohort 1, a medical monitor will review the accumulated safety and tolerability results to ensure there are no safety concerns with proceeding to the 100 mg dose (Cohorts 2 and 3), and to determine if a maximum tolerated dose (MTD) has been reached. If the MTD is reached, no dose escalation will occur. There will be an approximate 2-week period between Cohorts 1 and 2 to accommodate this safety review. A similar procedure will be used prior to proceeding to the 100 mg twice daily dose (Cohort 4).

If the medical monitor determines that it is safe to proceed to NBI-74788 100 mg, subjects in Cohort 2 will be administered NBI-74788 100 mg daily for 14 days. Dosing for Cohorts 3 and 4 may begin simultaneously with Cohort 2.

During the 14-day dosing period for any cohort, dosing may be postponed or halted if one or more subjects experience a severe or serious adverse event (AE), or if the type, frequency, or severity of AEs becomes unacceptable. If dosing is postponed, the medical monitor will review all available safety, tolerability, and PK data before allowing any further subjects to receive study drug.

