7. STUDY POPULATION

This study will be conducted in approximately 30 adult female and male subjects (18 to 50 years of age) with a documented medical diagnosis of classic 21-hydroxylase deficiency CAH. Subjects must meet all inclusion criteria and no exclusion criteria in order to be enrolled. Subjects who previously completed the current study in Cohort 1 or Cohort 2 may reenroll to participate in Cohorts 3 or 4 (in addition to new subjects). Subjects who reenroll and have had a stable medication regimen for CAH since their last visit in this study do not have to undergo screening; those who reenroll and have had a change to their medication regimen for CAH must undergo a second screening visit.

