7.3. Subject Identification and Replacement

Subjects will be identified during the study by their initials and a unique subject identification number (a hyphen may be used if the subject has no middle name). The subject initials and identification number will be written on all source documentation and laboratory specimens, and populated on all electronic Case Report Forms (eCRFs). Subjects who discontinue from the study will not be replaced.

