12.1. Analysis Sets

Data summaries for this study will be based on the safety analysis set, which will include all subjects who receive a dose of study drug.

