12.2. Sample Size

The sample size for this study is based on practical clinical considerations with no formal statistical power calculations.

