12.8. Safety Data

TEAEs, categorized by system organ class (SOC) and/or preferred term as defined by MedDRA, will be summarized by dose cohort as well as overall. A TEAE is defined as any AE that occurs after the first dose of study drug within a dose cohort. Any AE that occurred before the first dose of study drug will be considered a pretreatment AE. The TEAE tables will include the number and percentage of unique subjects experiencing each event. The TEAEs will also be tabulated in terms of the number and percentage of subjects experiencing events by relationship to study drug if a sufficient number of TEAEs is reported.

Data listings will be presented for SAEs, deaths, and AEs leading to premature discontinuation from the study.

Clinical laboratory data, vital sign measurements, ECG data, and other safety data will be summarized by dose cohort and timepoint (as appropriate) with descriptive statistics. Prior and concomitant medications and physical examination data will be presented in data listings.

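### Re-enrolment in Cohorts 3 and 4 is limited to subjects who completed Cohort 1 or 2, and the safety summaries do not separate them from new subjects, so adverse event rates there may be understated

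*Combined protocol and SAP*

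**What the plan says.** **Who may enter Cohorts 3 and 4.** Section 6.1 of the protocol states: "Subjects who previously completed the current study in Cohort 1 or Cohort 2 may reenroll to participate in Cohorts 3 or 4". This is "in addition to new subjects". Neither Section 6.1 nor Section 7 sets a minimum number of new subjects or a cap on re-enrolled ones.

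**Who cannot have completed.** Section 8.11.1 makes withdrawal mandatory when an adverse event becomes intolerable or when a cardiologist-verified QTcF exceeds 500 msec. An ECG abnormality, or liver or creatinine values above stated limits, may also lead to withdrawal, but only after case-by-case discussion with the medical monitor.

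**Numbers.** Section 7: "This study will be conducted in approximately 30 adult female and male subjects". Section 6.2: "Cohort 1 will consist of approximately 8 to 10 subjects". Table 1 gives the same 8 to 10 for Cohorts 2 and 3, and up to 8 for Cohort 4. Section 12.2: "The sample size for this study is based on practical clinical considerations with no formal statistical power calculations".

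**Analysis.** Section 12.1: "Data summaries for this study will be based on the safety analysis set". Under Section 12.8, treatment-emergent adverse events "will be summarized by dose cohort as well as overall", and listings are planned for serious events, deaths and events leading to discontinuation. Re-enrolment status governs consent, screening and exclusion criterion 18, but does not appear in Section 12. The disposition summary in Section 12.4 does not count it.

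**The concern.** The first objective in Section 5 is the safety and tolerability of the different regimens, and the natural reading of the tables runs across the cohort columns. Those columns need not hold comparable groups. Every subject in Cohorts 1 and 2 is on a first course. Cohorts 3 and 4 may include subjects who have come through 14 days on the drug, after those who could not tolerate it were removed.

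A flat or falling adverse event rate from 50 mg once daily to 200 mg per day could then arise partly from selection. The same holds between Cohorts 2 and 3, which share a nominal daily dose and differ in dosing time and food: a lower rate in Cohort 3 could reflect who was in it. As planned, the summary tables would not let a reader see how far this applies.

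**Working it through.** The plan has no power calculation to reproduce. Two questions can be checked: how much re-enrolment the stated numbers imply, and how far it could move the Cohort 4 rate.

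**1. Places against people (Table 1, Section 7)**

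- Cohort 4 empty: 3 × 8 = 24 to 3 × 10 = 30 places.
- Cohort 4 full: 24 + 8 = 32 to 30 + 8 = 38 places.
- If the figure of about 30 counts individuals, a full Cohort 4 implies 32 − 30 = 2 to 38 − 30 = 8 re-enrolments, across Cohorts 3 and 4 together.
- Cohorts 1 and 2 hold 16 to 20 subjects, so all 8 Cohort 4 places could go to completers. This fits the total: 10 + 10 + 10 = 30 individuals in Cohorts 1 to 3, of whom 8 return.
- Filling both later cohorts only with completers would leave 16 to 20 individuals, which does not fit about 30.

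**2. Effect on the Cohort 4 rate**

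The documents give no re-enrolment or intolerance rates, so these inputs are assumptions:

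- p: probability that a subject would not tolerate 100 mg twice daily, 10% to 30%.
- q: share of those subjects who would already have failed to complete Cohort 1 or 2, 0 to 100%.
- k: re-enrolled subjects among the 8 in Cohort 4, 0 to 8.

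Other reasons for not completing, and the choice to return, are taken as unrelated to tolerance.

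- Risk in a completer: p_c = p(1 − q) / (1 − pq)
- Expected Cohort 4 rate: [k·p_c + (8 − k)·p] / 8
- Chance of no event: (1 − p_c)^k × (1 − p)^(8 − k)

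For p = 20% and q = 50%: p_c = 0.20 × 0.50 / (1 − 0.10) = 0.10 / 0.90 = 11.1%.

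| Re-enrolled of 8 | Expected rate | Chance of no event |
|---|---|---|
| 0 | 20.0% | 16.8% |
| 2 | (2 × 0.111 + 6 × 0.20) / 8 = 17.8% | 20.7% |
| 4 | (4 × 0.111 + 4 × 0.20) / 8 = 15.6% | 25.6% |
| 8 | 11.1% | 39.0% |

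Over p = 10% to 30%, q = 25% to 50% and k = 2 to 8, the expected rate falls by between 0.6 points (p = 10%, q = 25%, k = 2: 10.0% to 9.4%) and 12.4 points (p = 30%, q = 50%, k = 8: 30.0% to 17.6%). With q = 0 or k = 0 the fall is zero.

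**3. Precision if the cohort is split**

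With no events among n subjects, the exact one-sided 95% upper limit is 1 − 0.05^(1/n): 31% for n = 8, 39% for n = 6, 53% for n = 4 and 78% for n = 2.

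**The case against.** The strongest reply is that nothing here shows a bias will occur. How many return, how many are withdrawn for intolerance and how far tolerance of once-daily dosing predicts tolerance of twice-daily dosing are all unknown. The analysis is descriptive, each regimen has its own column, and events leading to discontinuation are listed, so intolerance in Cohorts 1 and 2 would be on record. All of that stands. It limits the point to what may happen, but does not supply the missing count or split.

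Several stronger readings are tempting, and the documents do not support them:

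- **That re-enrolled subjects are proven tolerators.** They completed 50 or 100 mg once daily, not 200 mg per day. Toxicity that first appears at the higher dose is not screened out. Section 6.2 lets Cohort 4 start alongside Cohort 2, so the first returners may have taken only 50 mg.
- **That everyone with an abnormal laboratory or ECG finding is kept out.** Those withdrawals are discretionary. A subject kept on study completes and may return. Sections 8.8.2 and 8.8.3.1 update eligibility criteria only for subjects who undergo screening.
- **That both later cohorts have higher exposure.** Cohort 3 has Cohort 2's nominal daily dose, and the documents show no exposure figures comparing the meal conditions.
- **That returners carry no risk.** This needs q = 100%, meaning every susceptible subject is withdrawn at any dose. With k = 8 the expected rate is then zero by construction. Under that same assumption, with 15% susceptible, Cohorts 1 and 2 would show at least one case with probability 1 − 0.85^16 = 93% to 1 − 0.85^20 = 96%, so the signal would appear at the lower doses.
- **That the rule against replacing dropouts adds to the problem.** Section 7.3 does not affect who enters Cohorts 3 and 4.

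**Conclusion.** The gap is real but limited. Re-enrolment is restricted to completers, the stated numbers imply about 2 to 8 re-enrolments if Cohort 4 fills and 30 counts individuals, and Sections 12.4 and 12.8 neither count nor separate these subjects. The likely direction is to understate intolerance in Cohort 4 against Cohorts 1 and 2, and in Cohort 3 against Cohort 2.

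The size cannot be settled from the documents. In the central illustration (20% intolerance, half already removed) the understatement is 2.2, 4.4 or 8.9 percentage points with 2, 4 or 8 of 8 re-enrolled. It is nil if nobody returns or nobody is withdrawn for intolerance. Shifts of this size are small beside the sampling uncertainty in 8 subjects, but they run in one direction and would not be visible in the planned tables.

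A reader might infer that the plan will make 100 mg twice daily look safer than it is, or that these tables select a dose to carry forward. The first needs rates that the documents do not give. The second is not stated anywhere: Section 4.3 gives the purpose of Cohort 4 as comparing the effect of dosing schedules on biomarker response.

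**What to change.** - **Section 12.4:** report the number of new and re-enrolled subjects in each cohort.
- **Section 12.8:** for Cohorts 3 and 4, show treatment-emergent adverse events and discontinuations for adverse events by prior exposure (new; re-enrolled) beside the cohort total. Flag re-enrolled subjects in the safety listings.
- **Interpretation:** state that tolerability comparisons between cohorts are to be read with this selection in mind.

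Comparisons should not rest on the new-subject column alone. It may hold few or no subjects, and 0 events in 2 subjects is compatible with a rate of up to 78% (one-sided 95% limit). Show both columns and the total.

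The cost is a few table columns and a listing flag. Enrolment, dosing and sample size do not change. The drawback is small cells.

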6.2. Dose Escalation Procedure

Cohort 1 will consist of approximately 8 to 10 subjects who will receive a daily dose of NBI-74788 50 mg at approximately 2200 hours for 14 days (subjects will receive study drug at the site on Days 1, 2, and 14, and self-administer study drug at home on Days 3 to 13). Following the completion of Day 15 assessments for all subjects in Cohort 1, a medical monitor will review the accumulated safety and tolerability results to ensure there are no safety concerns with proceeding to the 100 mg dose (Cohorts 2 and 3), and to determine if a maximum tolerated dose (MTD) has been reached. If the MTD is reached, no dose escalation will occur. There will be an approximate 2-week period between Cohorts 1 and 2 to accommodate this safety review. A similar procedure will be used prior to proceeding to the 100 mg twice daily dose (Cohort 4).

If the medical monitor determines that it is safe to proceed to NBI-74788 100 mg, subjects in Cohort 2 will be administered NBI-74788 100 mg daily for 14 days. Dosing for Cohorts 3 and 4 may begin simultaneously with Cohort 2.

During the 14-day dosing period for any cohort, dosing may be postponed or halted if one or more subjects experience a severe or serious adverse event (AE), or if the type, frequency, or severity of AEs becomes unacceptable. If dosing is postponed, the medical monitor will review all available safety, tolerability, and PK data before allowing any further subjects to receive study drug.

7. STUDY POPULATION

This study will be conducted in approximately 30 adult female and male subjects (18 to 50 years of age) with a documented medical diagnosis of classic 21-hydroxylase deficiency CAH. Subjects must meet all inclusion criteria and no exclusion criteria in order to be enrolled. Subjects who previously completed the current study in Cohort 1 or Cohort 2 may reenroll to participate in Cohorts 3 or 4 (in addition to new subjects). Subjects who reenroll and have had a stable medication regimen for CAH since their last visit in this study do not have to undergo screening; those who reenroll and have had a change to their medication regimen for CAH must undergo a second screening visit.

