Subjects in Cohorts 3 and 4 will have a blood sample collected on Day 1 for (only for subjects who have not previously participated in Cohorts 1 or 2). Baseline safety assessments will be collected on Day 1 prior to the first dose of study drug. For Cohort 3, study drug (NBI-74788 100 mg) will be administered at home on Days 1 to 13 at approximately 1900 hours with each subject's evening meal. For Cohort 4, study drug (NBI-74788 100 mg) will be administered at home on Days 2 to 14 at approximately 0700 hours with each subject's breakfast and on Days 1 to 13 at approximately 1900 hours with each subjects' evening meal. For both cohorts, the Day 14 evening dose will be administered at the study site. Subjects will take their usual morning dose of concurrent steroidal treatments at approximately 1000 hours on Days 1 to 14. On Day 7 during the treatment period, PK, PD, and safety assessments will be conducted in an outpatient setting at the study center. Subjects will be admitted to the study center on Day 14 (last day of dosing). On Day 14, subjects will receive study drug in the study center at approximately 1900 hours with a standard (moderate fat/moderate calorie) evening meal. The subjects' usual morning dose of concurrent steroidal treatments will be administered after PK/PD samples are collected at approximately 1400 hours on Day 15. Subjects will be discharged from the study center the evening on Day 15 following completion of all studyrelated procedures.

Standard meals and snacks will be provided by the study center during the in-patient stays.

For all cohorts, follow-up visits on Days 21, 28, and 35 will be conducted at the study center or the subject's home by a qualified home healthcare provider (based on the subject's preference). A final study visit will be conducted at the study site approximately 5 weeks after the last dose of study drug (on Day 49 or early termination). There will be a visit window of -8 hours for Day 7, -8 hours/+3 days for Days 21, 28, and 35, and +7 days for the final study visit. Safety, tolerability, PK, and PD will be assessed at scheduled times throughout the study.

The study design schematic is shown in Figure 1.

Figure 1: Study Design Schematic

bid=twice daily.

Visits on Days 21 (+3 days), 28 (+3 days), and 35 (+3 days); final study visit on Day 49 (+7 days) or early termination.

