7.2. Subject Exclusion Criteria

Subjects will be excluded from the study if they:

- 1. Have a clinically significant unstable medical condition or chronic disease (including history of neurological, hepatic, renal, cardiovascular, gastrointestinal, pulmonary, psychiatric or endocrine disease [excluding CAH]), or malignancy that could confound interpretation of study outcome.
- 2. Had a clinically significant illness within 30 days of screening.

- Have a known or suspected diagnosis of any of the other known classic forms of CAH including 11β-hydroxylase deficiency, 17β-hydroxylase deficiency, 3β-hydroxysteroid dehydrogenase deficiency, P450 side-chain cleavage deficiency, or P450 oxidoreductase deficiency.
- Have a history that includes bilateral adrenalectomy, hypopituitarism, or other condition requiring daily therapy with orally administered glucocorticoids (eg, asthma, arthritis, or systemic lupus erythematosus).
- 5. Have any clinically significant acute or unstable chronic abnormal finding in physical examination, neurological assessment, vital signs, ECGs, or clinical laboratory tests, as determined by the investigator.
- 6. Are pregnant or lactating females.
- 7. Have a history of epilepsy or serious head injury (eg, traumatic brain injury or postconcussive syndrome).
- 8. Have a known history of long QT syndrome or cardiac tachy-arrhythmia.
- Have a screening or baseline (Day 1) average ECG corrected QT interval using Fridericia's formula (QTcF) of >450 msec (males) or >470 msec (females) or the presence of any clinically significant cardiac abnormality.
- 10. Have an exaggerated pharmacological sensitivity (ie, hypersensitivity) to any corticotropin releasing hormone antagonists.
- 11. Test positive at screening for hepatitis B surface antigen (HBsAg), hepatitis C antibody (HCV-Ab), or human immunodeficiency virus antibody (HIV-Ab), or have a history of a positive result.
- 12. Have a recent history (≤1 year before screening) of alcohol or drug abuse, or current evidence of substance dependence or abuse criteria.

- 18. Used any other investigational drug within 30 days or 5 half-lives (whichever is longer) before initial screening, or plans to use an investigational drug (other than the study drug) during the study. Subjects who previously completed the current study in Cohort 1 or Cohort 2 may reenroll to participate in Cohorts 3 or 4; these subjects do not need to meet this criterion with respect to NBI-74788.

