8.5.4. Clinical Laboratory Assessments

All clinical laboratory assessments will be conducted by a central laboratory, which will provide instructions and supplies to the study staff before study initiation. The instructions will be included in a laboratory manual. The laboratory test battery will include routine and screening laboratory tests. Laboratory samples will be collected in the following approximate amounts: 7.5 mL for hematology (including 4.5 mL for coagulation parameters), 5 mL for clinical chemistry, 10 mL for serology, 7 mL for PD, 2 mL for PK, and 4 mL for (a total of approximately 458.5 mL of blood will be collected over the course of the study from each subject).

Clinical laboratory assessments will be conducted at the following times:

- Screening.
- Day 1.
- Day 7.
- Day 15.
- Day 49 (or final study visit for subjects who terminate early).

The following clinical safety laboratory assays will be conducted:

Hematology: complete blood count including white blood cell count with differential, red blood cell count, hemoglobin, hematocrit, platelet count, mean corpuscular hemoglobin (MCH), mean corpuscular volume (MCV), mean corpuscular hemoglobin concentration (MCHC), red cell distribution width (RDW), mean platelet volume (MPV),

Clinical chemistry: sodium, potassium, calcium, magnesium, chloride, blood urea nitrogen, bicarbonate, creatinine, uric acid, albumin, alkaline phosphatase, lactate dehydrogenase, AST, ALT, gamma-glutamyl transferase (GGT), CK, myoglobin, total and conjugated bilirubin, total cholesterol, triglycerides, total protein, and glucose.

Urinalysis: specific gravity, nitrite, ketones, protein, urobilinogen, glucose, bilirubin, leukocyte esterase, occult blood, pH, and quantitative myoglobin. Microscopic examination of sediment will include evaluation for casts and crystals.

The following additional laboratory tests will be conducted:

FSH: Conducted at screening (postmenopausal females only).

Serology: Blood will be collected for HBsAg, HCV-Ab, and HIV-Ab testing at screening. The results of the HIV-Ab testing will be retained by the study site under confidential restriction.

Urine drug screen and alcohol breath test: The urine drug screen will test for amphetamines barbiturates, phencyclidine, benzodiazepines, cannabinoids, cocaine, and opiates. A urine drug screen and alcohol breath test will be conducted at screening, Day -7, Day 1, and Day 14. Urine

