8.8.1. Screening Period (Study Days -28 to -8)

Subjects who reenroll and have had a stable medication regimen for CAH since their last visit in this study (in Cohorts 1 or 2) do not have to undergo screening; those who reenroll and have had a change to their medication regimen for CAH must undergo a second screening visit. After providing subject informed consent, subjects will undergo screening procedures within 21 days of Day -7.

The following study evaluations and tasks will be performed during screening:

- Assess inclusion/exclusion criteria.
- Collect medical history.
- Perform a physical examination including height and weight.
- Collect vital signs.
- Perform 12-lead ECG in triplicate (1-3 minutes apart).
- Perform a serum pregnancy test (β -hCG) for female subjects of childbearing potential.
- Collect blood sample for FSH testing only if subject is postmenopausal.
- Collect blood sample for serology testing (HBsAg, HCV-Ab, and HIV-Ab).
- Collect blood sample for morning serum 17-OHP measurement between 0700 and 1000 hours (prior to first morning dose of hydrocortisone). Subject must have serum 17-OHP level ≥1,000 ng/dL to be enrolled in the study.
- Collect blood sample for hematology and clinical chemistry.

- Collect urine sample for urinalysis.
- Collect urine for drug screen (central laboratory) and perform alcohol breath test.
- Collect blood sample for other PD biomarkers (androstenedione, testosterone, cortisol, and ACTH).
- Administer the C-SSRS (Screening/Baseline version).
- AE monitoring.
- Record prior medications.

Eligible subjects will be instructed to return to the study center on Day -7.

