8.8.2. Day -7 to Day -6: 24-Hour Baseline Pharmacodynamics

Subjects who reenroll and do not undergo screening must provide subject informed consent.

Subjects who continue to meet eligibility requirements will return to the study center for a 24-hour in-patient stay, during which blood samples will be collected for PD analysis. Subjects will not take their usual morning dose of steroidal treatment until after the 1000 hours PD sample is collected on Day -6.

The following study evaluations and tasks will be performed on Day -7 to Day -6:

- Update inclusion/exclusion criteria and medical history (only for subjects who undergo screening).
- Collect vital signs.
- Perform a urine (for subjects who undergo screening) or serum (for subjects who did not undergo screening) pregnancy test (β-hCG) for female subjects of childbearing potential.
- Collect urine for drug screen and perform alcohol breath test. Urine testing kits will be provided by the central laboratory to confirm negative drug screen prior to PD collection. A separate urine sample will also be sent to the central laboratory for analysis.
- Collect blood samples for PD biomarkers (17-OHP, androstenedione, testosterone, cortisol, and ACTH) at: approximately 1845, 2000, 2100, 2200, 2300, 2400, 0100, 0200, 0400, 0600, 0800, 1000, 1200, 1400, 1800, 1900, and 2200 hours.
- Administer the C-SSRS (Screening/Baseline version) only for subjects who reenroll and who do not undergo screening.
- AE monitoring.
- Record prior medications.

Eligible subjects will be instructed to return to the study center on Day 1.

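### Re-enrolled subjects who skip screening have no limit on the age of their safety laboratory results, and their first new draw is on the day of the first dose

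*Combined protocol and SAP*

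**What the plan says.** **Waiver.** Section 7 allows completers to return: "Subjects who previously completed the current study in Cohort 1 or Cohort 2 may reenroll to participate in Cohorts 3 or 4". The condition for skipping screening is "Subjects who reenroll and have had a stable medication regimen for CAH since their last visit in this study do not have to undergo screening". The Synopsis, Sections 6.1 and 8.8.1 and Table 3 footnote a use the same condition. None adds a time limit.

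**Subjects who are screened.** Section 8.8.1 states that "subjects will undergo screening procedures within 21 days of Day -7". That visit includes hematology, chemistry and urinalysis.

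**Day -7 to Day -6.** For Cohorts 3 and 4 the blood work in Section 8.8.2 is pharmacodynamic: "Collect blood samples for PD biomarkers (17-OHP, androstenedione, testosterone, cortisol, and ACTH) at: approximately 1845" and at later times. Waived subjects also have a serum pregnancy test. Table 3 marks no clinical laboratory tests here.

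**Day 1.** Section 8.8.3.1 schedules hematology, chemistry and urinalysis, and Table 3 footnote k includes coagulation in the panel. Section 8.5.4 says "All clinical laboratory assessments will be conducted by a central laboratory". Section 6.1 then has "For Cohort 3, study drug (NBI-74788 100 mg) will be administered at home on Days 1 to 13 at approximately 1900 hours". Cohort 4 also starts at about 1900 hours on Day 1, at home (Sections 6.1 and 9.3).

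**Eligibility.** Section 7 requires every subject to meet all criteria. Exclusion 5 bars subjects who "Have any clinically significant acute or unstable chronic abnormal finding in physical examination, neurological assessment, vital signs, ECGs, or clinical laboratory tests", in the investigator's judgment. Sections 8.8.2 and 8.8.3.1 schedule the update of criteria and medical history only for subjects who undergo screening.

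**The concern.** Exclusion 5 depends partly on laboratory findings. Screening gives the investigator recent ones for a screened subject. For a waived subject the latest scheduled results are those of the final visit in the earlier course, and the plan does not say how recent they must be. Stability of the CAH regimen says nothing about liver, renal, muscle or coagulation values, and a new illness or a change in another medicine does not trigger screening.

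The Day 1 draw does not close the gap as written. Table 3 footnote c makes predose Day 1 values the baseline, and nothing makes the first dose wait for them. The plan handles other checks differently. For waived subjects it moves the serum pregnancy test and the Screening/Baseline C-SSRS to Day -7, and for everyone it confirms the drug screen with kits at the site before dosing. The safety laboratory panel was given neither route.

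At stake is an entry check for subjects who go from 50 or 100 mg per day to 100 or 200 mg per day, with the first dose at home. Section 8.11.1 lists liver and creatinine values as possible grounds for withdrawal. A waived subject could already exceed one of them at the first dose without anyone knowing.

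**Working it through.** No power or error-rate calculation is involved; Section 12.2 says "The sample size for this study is based on practical clinical considerations with no formal statistical power calculations". The check is calendar arithmetic. Day 1 is one week after Day -7 (Table 3 footnote c), so there is no Day 0. From a negative day -a to a positive day b the interval is a + b - 1 days.

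**Step 1: does the stated duration limit the gap?** Section 8.9 gives an additional 8 to 11 weeks for subjects who re-enroll.
- Without screening, Day -7 to Day 49: 7 + 49 - 1 = 55 days; 55/7 = 7.9 weeks.
- With screening, Day -28 to Day 49: 28 + 49 - 1 = 76 days; 76/7 = 10.9 weeks.

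Both ends of the stated range are reproduced by the visit schedule alone. The figure counts time inside the second course and does not limit the time between courses.

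**Step 2: age of the results on Day 1, screened subject.** The window is Day -28 to Day -8.
- Oldest: 28 + 1 - 1 = 28 days.
- Newest: 8 + 1 - 1 = 8 days.

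**Step 3: age on the new Day 1, waived subject.** Let g be the gap in weeks from the earlier final visit to the new Day -7. Age = 7g + 7 days. The plan gives no value of g, so these are assumptions that show the range:

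| Assumed gap g (weeks) | Age on Day 1 (days) | Relative to the 28-day maximum |
|---|---|---|
| 0 | 7 | 0.25 |
| 4 | 35 | 1.25 |
| 13 | 98 | 3.5 |
| 26 | 189 | 6.75 |
| 52 | 371 | 13.25 |

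The age exceeds 28 days once 7g + 7 > 28, that is, for g > 3 weeks. A limit of 21 days before Day -7 therefore puts waived and screened subjects on the same footing.

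**Step 4: new information before the first dose, waived subject** (Sections 8.8.2 and 8.8.3.1).
- Day -7: vital signs, pharmacodynamic biomarkers, serum pregnancy test, drug and alcohol tests, C-SSRS.
- Day 1: physical examination, vital signs, triplicate ECG, urine pregnancy test, drug and alcohol tests, BPRS, C-SSRS; safety laboratory samples drawn.

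The Day 1 examination, vital signs and ECG cover the other parts of exclusion 5. What remains is hematology, coagulation, chemistry and urinalysis.

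**The case against.** The best defense is that exclusion 5 still binds. Section 7 exempts no one from the criteria, the judgment is the investigator's, and the investigator holds the earlier final-visit results and may order tests. These subjects have completed a 14-day course with laboratory tests on Days 1, 7, 15 and 49, and tests recur on Day 7 of the new course. Screened subjects, too, are dosed with no required review of their Day 1 results. All of this is true and lowers the stakes. It does not supply a current result, and the screened subject has a backstop of at most 28 days.

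Two further points stand as limits. Neither the central laboratory's turnaround nor the time of the Day 1 visit is stated, so late results are an inference, although no step requires review even if results are quick. Exclusions 13 to 17 and 22 are not visible in the public text, so a relevant laboratory rule there cannot be ruled out.

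A reader might also infer that an undetected abnormality would distort change-from-baseline safety summaries. The documents do not support that. Section 12.8 plans descriptive summaries of laboratory data by cohort and timepoint, and change from predose is specified only for pharmacodynamic measures (Section 12.7). An abnormality present before dosing belongs in the baseline in any case.

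**Conclusion.** The gap is real and narrow. Followed exactly, the plan lets a waived subject take the first dose with no current hematology, coagulation, chemistry or urinalysis result. The latest scheduled results are at least about 7 days old with no written maximum, against 28 days for a screened subject. In practice the length of the study bounds the age; the gaps used above are illustrations, not predictions.

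The number of subjects affected is unknown. A reader might add up the places in Cohorts 3 and 4 (8 to 10 plus up to 8, so 16 to 18 with Cohort 4 full) and treat them all as exposed. That would need every place to be filled by a waived completer, whereas Section 7 describes re-enrolment as being in addition to new subjects. With Cohort 4 full, the four cohorts hold 3 × 8 + 8 = 32 to 3 × 10 + 8 = 38 places, against approximately 30 subjects. If 30 counts distinct people, that implies about 2 to 8 re-enrolments, but the plan does not say whether it counts people or places.

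It would also go too far to say that exclusion 5 cannot be applied to these subjects. Only its laboratory part lacks a current basis, and only when the gap is long.

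**What to change.** In Sections 6.1, 7, 8.5.4, 8.8.1 and 8.8.2 and in Table 3, with the matching Synopsis text, add a recency condition to the waiver using the 21-day window already in Section 8.8.1. If the earlier final-visit laboratory tests fall within 21 days of the new Day -7, they serve as the entry results. If they are older, do one of the following:

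- draw the existing safety laboratory panel during the Day -7 to Day -6 stay, where blood is already being sampled a week before dosing; or
- require the screening visit already described in Section 8.8.1.

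In all cases, state that the results are reviewed against exclusion 5 before Day 1 dosing. That review has to be written in for waived subjects, because the scheduled criteria update now leaves them out.

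The first option is lighter: one panel at an existing stay, with no repeat of serology or the qualifying 17-OHP. By the volumes in Section 8.5.4 it takes 7.5 + 5 = 12.5 mL more blood from the subject, as these tests do at screening, and the stated total should be checked. The second option costs late returners a visit. Neither adds a new type of procedure.
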